#### **Study procedures:**

Thoracic epidural placement will occur in the preoperative period. Both the rectus sheath block and the surgeon infiltration will occur at the end of the case. All procedures will be done using sterile technique with masks, hats, and sterile gloves. Thoracic epidurals and rectus sheath block will be placed under the supervision of the attending anesthesiologist on the acute pain service. Surgeon infiltration will be performed by the surgeon.

Patients will be randomized to one of the four arms by the research randomizer. On the day of surgery, the Principal Investigator will inform the person doing the block as to what group the patients are randomized to.

Thoracic epidural will be performed around T9-T10 interspace since that correlates with surgical incision dermatomes. Utilizing the loss-of-resistance technique, an 18-gauge needle will be inserted in the midline between the lumbar spinous processes and advanced until loss-of-resistance is felt. A small amount of preservative-free saline will be injected to ensure the location in the epidural space. After careful aspiration, a test dose of 2-3 mL local anesthetic containing diluted epinephrine will be injected and the heart rate will be monitored in case of accidental placement in an epidural vein.

---

Rectus sheath block will be performed at 4 locations below the rectus abdominis muscle, using an ultrasound. The locations will be both left and right abdomen, above and below the umbilical region.

Surgical wound infiltration will be performed by the surgeon at the end of the case. It will be performed via a direct technique. In the direct technique, anesthetic is injected after careful aspiration in small boluses into the subfascial tissues until the wound is adequately anesthetized.

Opioid usage at 1, 24, 48, 72, and 96 hours after the block will be recorded by a member of the research team. Pain scores at rest and on movement (knee flexion) will be measured by the investigator using Visual Analog Scale (VAS). VAS will measure pain from a scale of 0-10. Nausea will be measured using a categorical scoring system (none=0; mild=1; moderate=2; severe=3). Nausea score will be reported by the patients. Anti-emetic usage will also be recorded. Sedation scores will also be assessed by a member of the study team using a sedation scale. Hospital length of stay (LOS) will be collected via EMR of the admission and discharge date to calculate the LOS. We will also measure time to first flatus, postoperative creatinine, incidence of hypotension (defined as BP decrease of more than 20% from morning of surgery), incidence of respiratory depression (defined by nursing report or naloxone use), and ambulation activity (anytime out of bed (up in chair, to bathroom and walking in hall with PT/nurse) will also be recorded daily. It will be recorded as yes/no.

All these parameters will be measured at 1, 24, 48, 72, and 96 hours after the cystectomy.

All patients will complete a phone survey approximately 6 months after surgery to assess for pain and how it impacts their daily function. This is meant to assess for the incidence of chronic post-op pain after cystectomy with all the different pain interventions. The survey will measure how their pain interfere with their general activity, mood, walking ability, normal work, relations with other people, sleep and enjoyment of life. If after four attempts to contact the patient are unsuccessful, the survey will not be completed; this will not be considered a deviation as the survey is not critical to the overall data collection.

Data management will include quality assurance and quality control measures. All collected data will be monitored by a data and safety monitoring group independent from the research team. Data quality, subject recruitment, accrual,-retention, outcome and adverse event data, assessment of scientific reports or therapeutic development, results of related studies that may impact subject safety and procedures designed to protect the privacy of subjects will be monitored at least annually.

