## 2.0 Rational and Specific Aims

All of the pain control modalities in this study have been used as postoperative analgesia in prior studies. The specific aim of this study is to compare the difference between the pain control methods in achieving the following:

1. Decreased opioid requirements
2. Improved postoperative VAS (Visual Analog Scale) pain scores
3. Decreased opioid side effects (Nausea, sedation, ileus, respiratory depression)
4. Decreased hospital length of stay (LOS)

The primary endpoint of this study will be VAS (Visual Analog Scale) pain score at both resting and with movement. The VAS Visual Analog Scale) pain score will be measured at 24, 48, 72 and 96 hours under an advanced recovery perioperative care pathway.

The secondary endpoint includes intravenous opioid consumption, opioid side effects (nausea, sedation, ileus, respiratory depression), and LOS. Hospital length of stay (LOS) will be collected via EMR of the admission and discharge date to calculate the LOS. The IV and PO opioid doses will be quantified at 1, 24, 48, 72, and 96 hours. All the opioid consumption (both PO and IV) will be converted to PO morphine equivalent for analysis. We will also measure postoperative nausea and sedation scores at 1, 24, 48, 72, and 96 hours. Nausea will be measured on a 4-point scale: none, mild, moderate or severe. This is collected as patient reported as well as per nursing documentation. Sedation score is also reported on a 4-point scale: awake/alert, quietly awake, asleep/arousable or deep sleep. This is collected as an observation by nurse coordinator/staff. We will access patient's satisfaction at 24, 48, 72 and 96 hours. This will be measured on a 5-point scale; very unsatisfied, unsatisfied, neutral, satisfied and very satisfied. We will also measure time to first flatus, postoperative creatinine, incidence of hypotension (defined as BP decrease of more than 20%), incidence of respiratory depression, and ambulation activity.

Ambulation is defined as anytime out of bed (up in chair, to bathroom and walking in hall with PT/nurse) activity will also be recorded daily. It will be recorded as yes/no.

---

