## **7.0 Statistical consideration**

Primary outcome: VAS score with movement at 48 and 72 hours

Primary Research Hypothesis: Thoracic epidural will provide lower postoperative pain scores compared to each of the other three methods used for cystectomy as measured by VAS scores at 24, 48, 72, and 96 hours under an enhanced recovery perioperative care pathway.

Secondary outcomes: Narcotic usage after 1, 24, 48, 72, and 96 hours. Pain scores using VAS at rest and on knee flexion at 1, 24, 48, 72, and 96 hours. Nausea scores at 1, 24, 48, 72, and 96 hours. Sedation scores at 1, 24, 48, 72, and 96 hours. Time to first flatus, postoperative creatinine, hospital length of stay (hospital length of stay (LOS) will be collected via EMR of the admission and discharge date to calculate the LOS), ileus, hypotension (defined as BP decrease of more than 20%), and ambulation/anytime out of bed (up in chair, to bathroom and walking in hall with PT/nurse) activity will also be recorded daily. It will be recorded as yes/no.

If the patient is discharged within 96 hours, every effort will be made to obtain data points, but we will not consider these data point deviations since our 96-hour data point will not change the integrity of the study.

Secondary Research Hypotheses: Thoracic epidural will show improved patient satisfaction scores and decreased nausea and sedation scores compared to each of the other three treatments.

Statistical analysis will be performed using a standard statistical program (SAS or SPSS). All data will be summarized (means, standard deviations, standard errors, and ranges for continuous variables; frequencies and percentages for categorical variables) by group. Demographic data will be compared between the four groups using ANOVA or chi-square tests as appropriate. The primary outcome, VAS ( Visual Analog Scale) at 48 and 72 hours, will be compared between the

groups using repeated measures ANOVA; the model will include fixed effects for group, time, and the group by time interaction and random effects to allow correlations between the two times and different variances for the two times.

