Pain and satisfaction scores and opioid usage over time will be analyzed using repeated measures ANOVA. Nausea and sedation scores will be compared between groups at each time point using Mantel-Haenszel chi-square tests for ordered categorical data. Time to first flatus, postoperative creatinine, and LOS will be compared between the groups using one-way ANOVA. The binary outcomes of incidence of ileus, hypotension (defined as BP decrease of more than 20%), and incidence of respiratory depression will be analyzed using logistic regression. Distributions of the continuous variables will be examined, and a transformation of the data (e.g. natural logarithm) or nonparametric tests will be used as necessary. A 5% significance level will be used for all comparisons.

Based on prior studies, the coefficient of variation for the VAS ( Visual Analog Scale) score at 48 and 72 hours is estimated to be 0.70. With a sample size of 40 per group the study will have 80% power to detect a ratio of means of 1.5 for VAS score between any two of the four treatment groups, assuming two-sided tests each conducted at a 5% significance level.

All patients will receive a phone survey approximately 6 months after surgery to assess for pain, quality of life, and satisfaction of hospital stay. Quality of life is measured by how their pain interferes with their general activity, mood, walking ability, normal work, relations with other people, sleep and enjoyment of life. If after four attempts to contact the patient are unsuccessful, the survey will not be completed; this will not be considered a deviation as the survey is not critical to the overall data collection.

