## **9.0 Follow-up/record retention**

The study will start in August of 2019 and will end when a sample size of 160 subjects is achieved. Since Indiana University Hospital performs a large number (~180) of cystectomies per year, the estimated time frame to enroll 160 study subjects is 24 months. After 160 subjects have been enrolled, the study will be stopped and the data collected will be analyzed using statistical methods.

Three years after completion of the study, all study papers with patient identifiers will be shredded and only data without any patient identifiers will be retained by the research team for an indefinite time.

Butterworth Iv, John F., David C. Mackey, and John D. Wasnick. "Spinal, Epidural, &Amp; Caudal Blocks." In *Morgan &Amp; Mikhail's Clinical Anesthesiology, 6e*. New York, NY: McGraw-Hill Education, 2018.

de Boer, H. D., O. Detriché, and P. Forget. "Opioid-Related Side Effects: Postoperative Ileus, Urinary Retention, Nausea and Vomiting, and Shivering. A Review of the Literature." [In eng]. *Best Pract Res Clin Anaesthesiol* 31, no. 4 (Dec 2017): 499-504.

Guo, Q., R. Li, L. Wang, D. Zhang, and Y. Ma. "Transversus Abdominis Plane Block Versus Local Anaesthetic Wound Infiltration for Postoperative Analgesia: A Systematic Review and Meta-Analysis." [In eng]. *Int J Clin Exp Med* 8, no. 10 (2015): 17343-52.

Hou, X., Z. Luo, H. Wang, Y. Zhan, L. Yang, and L. Li. "[Effect of Adductor Canal Block Combined with Local Infiltration Anesthesia on Rehabilitation of Primary Total Knee Arthroplasty]." [In chi]. *Zhongguo Xiu Fu Chong Jian Wai Ke Za Zhi* 32, no. 8 (Aug 1 2018): 1006-11.

Kalogera, E., J. N. Bakkum-Gamez, A. L. Weaver, J. P. Moriarty, B. J. Borah, C. L. Langstraat, C. J. Jankowski, et al. "Abdominal Incision Injection of Liposomal Bupivacaine and Opioid Use after Laparotomy for Gynecologic Malignancies." [In eng]. *Obstet Gynecol* 128, no. 5 (Nov 2016): 1009-17.

Ladjevic, N., I. Likic-Ladjevic, Z. Dzamic, M. Acimovic, D. Dragicevic, and O. Durutovic. "Combined General and Epidural Anaesthesia Versus General Anaesthesia for Radical Cystectomy." [In eng]. *Acta Chir Iugosl* 54, no. 4 (2007): 89-91.

Mazul-Sunko, B., I. Gilja, M. Jelisavac, I. Kozul, D. Troha, N. Osmancevic, A. El-Saleh, et al. "Thoracic Epidural Analgesia for Radical Cystectomy Improves Bowel Function Even in Traditional Perioperative Care: A Retrospective Study in Eighty-Five Patients." [In eng]. *Acta Clin Croat* 53, no. 3 (Sep 2014): 319-25.

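### Opioid use has two conflicting time origins; timed from the block, the epidural arm's clock starts before surgery and the other arms' clocks at its end

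*Combined protocol and SAP*

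**What the plan says.** The Study procedures part of section 4.0 contains both origins. For opioids alone it says "Opioid usage at 1, 24, 48, 72, and 96 hours after the block will be recorded by a member of the research team". It then describes VAS, nausea, sedation and the remaining measures, and closes with "All these parameters will be measured at 1, 24, 48, 72, and 96 hours after the cystectomy".

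The same part fixes when each block happens. For the epidural: "Thoracic epidural placement will occur in the preoperative period". For the other arms: "Both the rectus sheath block and the surgeon infiltration will occur at the end of the case".

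The other mentions of opioid timing give no origin. Section 2.0 has "The IV and PO opioid doses will be quantified at 1, 24, 48, 72, and 96 hours". Section 7.0 lists "Narcotic usage after 1, 24, 48, 72, and 96 hours" among the secondary outcomes, and describes the analysis as "Pain and satisfaction scores and opioid usage over time will be analyzed using repeated measures ANOVA".

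**The concern.** One endpoint has two time origins, and they differ by arm. In the rectus sheath and the two infiltration arms, the block and the end of surgery are close together, so either sentence gives much the same clock. In the epidural arm, the block precedes the end of surgery by the time from catheter placement to the end of the operation. Staff who follow the opioid sentence literally would comply with the protocol and still record the epidural arm on an earlier clock.

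The epidural arm is the one that section 7.0 sets against each of the other three. Opioid requirement is the first specific aim and a named secondary endpoint. Randomization does not remove the problem, because the shift comes from the assigned treatment. A group effect, or a group-by-time effect in the repeated measures model, could then partly reflect the clock.

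**Working it through.** **The texts side by side**

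| Place | Opioid time origin |
|---|---|
| Section 4.0, Study procedures, opioid sentence | The block |
| Section 4.0, Study procedures, closing sentence | The cystectomy |
| Section 2.0 | None given |
| Section 7.0, outcome list and analysis | None given |

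The plan offers no figure for this point. Its one design figure is 80% power for VAS. That figure reproduces on the log scale with CV 0.70, ratio 1.5 and 40 per group: SD = √ln(1 + 0.70²) = 0.631, difference = ln 1.5 = 0.405, power 80.9% by noncentral t. It does not depend on the opioid clock.

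**Inputs for the size of the shift**

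- Time points T = 1, 24, 48, 72 and 96 h (sections 2.0, 4.0 and 7.0).
- Offset h = hours from epidural placement to end of surgery. The documents give neither an operating time nor a placement time, so 3 to 8 h is an assumption.
- In the other three arms the offset is taken as about 0.

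**Formulas, if the block clock is used**

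- Position of a reading relative to the end of surgery = T − h.
- Shortfall in postoperative hours up to T, if totals are cumulative = h / T.
- If totals are per interval, the epidural 24–48 h window covers postoperative hours (24 − h) to (48 − h).

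| h | 1-h reading | Postoperative hours in first 24 h | Shortfall at 24 h | 48 h | 72 h | 96 h | Epidural 24–48 h window, postoperative hours |
|---|---|---|---|---|---|---|---|
| 3 | 2 h before end | 21 | 12.5% | 6.25% | 4.2% | 3.1% | 21–45 |
| 4 | 3 h before end | 20 | 16.7% | 8.3% | 5.6% | 4.2% | 20–44 |
| 6 | 5 h before end | 18 | 25.0% | 12.5% | 8.3% | 6.25% | 18–42 |
| 8 | 7 h before end | 16 | 33.3% | 16.7% | 11.1% | 8.3% | 16–40 |

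For example, with h = 8: 24 − 8 = 16 postoperative hours, and 8/24 = 33.3%. The 1-h reading precedes the end of surgery for any h above 1. The first 24 h is affected whether totals are cumulative or per interval. The 48, 72 and 96 h columns apply only to cumulative totals, and the plan does not say which it uses.

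**Direction.** Fewer postoperative hours would lower the epidural total. Opioid given during surgery, if counted, would raise it, because on this clock it falls inside the epidural window but mostly before time zero in the other arms. The documents do not say whether such opioid counts, so the net direction cannot be determined.

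**If the cystectomy clock is used** and means end of surgery, all four arms share one origin and the shift is zero.

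**The case against.** The best defence is that the closing sentence governs. It comes last, covers every measure listed before it and uses the same five times, and opioid use is the first item in that list. Section 2.0 places the opioid times directly before postoperative nausea and sedation scores on the same schedule, which suggests one shared postoperative clock. The block reading also gives an odd result: a 1-h epidural value taken during surgery. The block wording may simply be loose drafting that suits three of the four arms.

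That reading is plausible, but no passage confirms it. The opioid sentence is the specific one. The closing sentence is a loose catch-all, since its list includes length of stay and time to first flatus, which cannot be measured at five fixed times. A data collector could reasonably follow either.

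Other objections limit the point without removing it:

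- Every percentage rests on an assumed offset. They are percentages of hours, and no effect on a conclusion has been demonstrated.
- The practical conflict is confined to the epidural arm.
- Section 4.0 places the liposomal infiltration before abdominal wall closure, so even the end-of-case arms are not timed identically. That difference should be small beside the epidural offset.
- Whether totals are cumulative or per interval is missing detail, separate from the contradiction.

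**Conclusion.** The concern holds. The plan contradicts itself on the opioid time origin, and one of its two stated rules, followed literally, would misalign the epidural arm with the other three.

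The effect is conditional on that rule being used. With an assumed offset of 3 to 8 h, the main damage is at 1 h, where the epidural value is not postoperative at all, and over the first 24 h, where the arm has 12.5% to 33% fewer postoperative hours. Any cumulative shortfall shrinks to about 3% to 8% by 96 h. Per-interval totals would keep their length after 24 h but cover earlier postoperative hours.

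The reach is limited to comparisons of opioid use that involve the epidural arm. Comparisons among the other three arms are essentially unaffected. VAS is timed only by the cystectomy sentence, so the primary outcome is untouched. This should be corrected, but it does not threaten the primary analysis. Confidence in the textual conflict is high; the size and direction of any bias are uncertain.

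**What to change.** Set one time zero common to all arms and all timed outcomes, such as end of surgery. In the Study procedures text, replace the block as the opioid origin with end of surgery, and define the cystectomy origin in the closing sentence as that same moment. Keep opioid given before time zero out of the postoperative totals and report it separately. While amending, it would help to state whether totals are cumulative or per interval, though the correction does not depend on this.

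The cost is a short wording amendment to two sentences, a recorded surgery-end time for each patient, and a separate line for opioid given before time zero. No treatment changes. Section 9.0 says "The study will start in August of 2019 and will end when a sample size of 160 subjects is achieved", and this version is dated 21 October 2019, so some patients may already have been enrolled. The documents do not show whether any were recorded on the block clock; totals for any who were would need re-deriving.

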## **5.0 Reporting of Adverse Events**

---

 Q. Guo et al., "Transversus Abdominis Plane Block Versus Local Anaesthetic Wound Infiltration for Postoperative Analgesia: A Systematic Review and Meta-Analysis," *Int J Clin Exp Med* 8, no. 10 (2015).

Patients will be monitored by the primary team during the postoperative period, and any adverse events or unanticipated problems such as local anesthetic toxicity or epidural hematoma formation or nerve damage will be reported to the acute pain service and research team. All adverse events or unanticipated problems that meet the criteria for prompt reporting will be reported to the IRB within 5 business days.

## **6.0 Study withdrawal/DC**

The patient can withdraw from the study at any time by contacting the research team or acute pain anesthesia resident. In such an event, patient may still have access to all the IV and oral pain medications. Anesthesia acute pain team will continue to follow the patient for 24 hours. After 24 hours, the anesthesia acute pain team will sign off and all further pain management will be done by the primary team.

## **7.0 Statistical consideration**

Primary outcome: VAS score with movement at 48 and 72 hours

Primary Research Hypothesis: Thoracic epidural will provide lower postoperative pain scores compared to each of the other three methods used for cystectomy as measured by VAS scores at 24, 48, 72, and 96 hours under an enhanced recovery perioperative care pathway.

Secondary outcomes: Narcotic usage after 1, 24, 48, 72, and 96 hours. Pain scores using VAS at rest and on knee flexion at 1, 24, 48, 72, and 96 hours. Nausea scores at 1, 24, 48, 72, and 96 hours. Sedation scores at 1, 24, 48, 72, and 96 hours. Time to first flatus, postoperative creatinine, hospital length of stay (hospital length of stay (LOS) will be collected via EMR of the admission and discharge date to calculate the LOS), ileus, hypotension (defined as BP decrease of more than 20%), and ambulation/anytime out of bed (up in chair, to bathroom and walking in hall with PT/nurse) activity will also be recorded daily. It will be recorded as yes/no.

If the patient is discharged within 96 hours, every effort will be made to obtain data points, but we will not consider these data point deviations since our 96-hour data point will not change the integrity of the study.

Secondary Research Hypotheses: Thoracic epidural will show improved patient satisfaction scores and decreased nausea and sedation scores compared to each of the other three treatments.

Statistical analysis will be performed using a standard statistical program (SAS or SPSS). All data will be summarized (means, standard deviations, standard errors, and ranges for continuous variables; frequencies and percentages for categorical variables) by group. Demographic data will be compared between the four groups using ANOVA or chi-square tests as appropriate. The primary outcome, VAS ( Visual Analog Scale) at 48 and 72 hours, will be compared between the

groups using repeated measures ANOVA; the model will include fixed effects for group, time, and the group by time interaction and random effects to allow correlations between the two times and different variances for the two times.

Pain and satisfaction scores and opioid usage over time will be analyzed using repeated measures ANOVA. Nausea and sedation scores will be compared between groups at each time point using Mantel-Haenszel chi-square tests for ordered categorical data. Time to first flatus, postoperative creatinine, and LOS will be compared between the groups using one-way ANOVA. The binary outcomes of incidence of ileus, hypotension (defined as BP decrease of more than 20%), and incidence of respiratory depression will be analyzed using logistic regression. Distributions of the continuous variables will be examined, and a transformation of the data (e.g. natural logarithm) or nonparametric tests will be used as necessary. A 5% significance level will be used for all comparisons.

Based on prior studies, the coefficient of variation for the VAS ( Visual Analog Scale) score at 48 and 72 hours is estimated to be 0.70. With a sample size of 40 per group the study will have 80% power to detect a ratio of means of 1.5 for VAS score between any two of the four treatment groups, assuming two-sided tests each conducted at a 5% significance level.

All patients will receive a phone survey approximately 6 months after surgery to assess for pain, quality of life, and satisfaction of hospital stay. Quality of life is measured by how their pain interferes with their general activity, mood, walking ability, normal work, relations with other people, sleep and enjoyment of life. If after four attempts to contact the patient are unsuccessful, the survey will not be completed; this will not be considered a deviation as the survey is not critical to the overall data collection.

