### **3.0 Inclusion/Exclusion**

Inclusion criteria:

- Patients undergoing cystectomy surgery
- ASA class 1, 2, 3 or 4
- Age 18 or older, male or female
- Desires Regional anesthesia for postoperative pain control

Exclusion criteria:

- Any contraindication for thoracic epidural, such as coagulopathic states or pre-existing hardware in the thoracic epidural space.
- History of substance abuse in the past 6 months.
- Patients on more than 30mg morphine equivalents of opioids daily.
- Any physical, mental or medical conditions which in the opinion of the investigators, may confound quantifying postoperative pain resulting from surgery.
- Known allergy or other contraindications to the study medications (Acetaminophen, Gabapentin, Bupivacaine, Hydromorphone).
- Postoperative intubation.
- Any patient with history of neuropathic bowel or bladder dysfunction

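### The primary repeated-measures model leaves out age and sex, which are known for every patient: a cheap missed efficiency gain, not an error

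*Combined protocol and SAP*

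**What the plan says.** Section 7.0 (Statistical consideration) of the combined protocol and SAP defines the endpoint: "Primary outcome: VAS score with movement at 48 and 72 hours". It is analysed by repeated measures ANOVA. On the fixed part, "the model will include fixed effects for group, time, and the group by time interaction". On the within-patient part, the plan adds "random effects to allow correlations between the two times and different variances for the two times". No baseline variable enters this model, and none is named for the secondary analyses.

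The same section gives baseline data two uses: all data are summarised by group, and "Demographic data will be compared between the four groups using ANOVA or chi-square tests as appropriate".

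Section 3.0 (Inclusion/Exclusion) sets a minimum age of 18 and admits both sexes, so both items are known for every patient at entry. On opioids it excludes "Patients on more than 30mg morphine equivalents of opioids daily". That requires a check against a threshold. Neither section 2.0, nor the study procedures in section 4.0, nor section 7.0 lists the preoperative opioid dose as a recorded variable. Postoperative opioid use is recorded from 1 hour onward. Section 4.0 describes computer randomisation to four groups of 40 and mentions no stratification.

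**The concern.** In a randomised comparison of a continuous outcome, adjusting for a baseline variable that predicts the outcome reduces residual variance. It also takes account of the modelled part of any chance imbalance between arms. Here neither the randomisation, as described, nor the analysis uses baseline information. Comparing demographics between arms does not do the same job, because it leaves the treatment estimate and its standard error unchanged.

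At stake is the width of the interval around each pairwise contrast with 40 patients per arm. The planned power sits only just above its target, and section 7.0 states no allowance for missing outcomes, so a few points of power would be useful if they are there to be had.

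**Working it through.** **Inputs from section 7.0**
- Variability: "the coefficient of variation for the VAS ( Visual Analog Scale) score at 48 and 72 hours is estimated to be 0.70".
- Effect and size: "With a sample size of 40 per group the study will have 80% power to detect a ratio of means of 1.5 for VAS score".
- Testing: "assuming two-sided tests each conducted at a 5% significance level".

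**Input not in the documents**
- R2, the share of VAS variance explained by the covariates. It is assumed, over 0 to 0.20.

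**Step 1: reproduce the stated power, without adjustment.** Work on the log scale, since the effect is a ratio of means.
- Log-scale SD = sqrt(ln(1 + 0.70²)) = sqrt(ln 1.49) = 0.6315.
- Difference = ln 1.5 = 0.4055.
- Standard error = 0.6315 × sqrt(2/40) = 0.1412.
- Noncentrality = 0.4055 / 0.1412 = 2.871.
- Noncentral t, two-sided 5%: 80.9% with 78 df (two arms alone) and 81.4% with 156 df (four arms pooled, 160 − 4).
- The normal approximation gives 81.9%, with 39 per group needed for 80%.

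The plan's 80% is therefore the power of an unadjusted comparison, and it matches the planned model. Like the plan's own figure, this treats each contrast as a single comparison of two means.

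**Step 2: charge for the covariates.** With three covariates the error df fall from 156 to 153. The expected inflation of the contrast's variance from estimating them is 155/152 = 1.020, about 2%.

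**Step 3: adjusted power.** The noncentrality becomes 0.4055 / [0.6315 × sqrt(1 − R2) × sqrt(2/40) × sqrt(155/152)], with 153 df. The comparator is 81.4% (unadjusted, pooled df).

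| Assumed R2 | Noncentrality | Power | Change from 81.4% |
|---|---|---|---|
| 0 | 2.844 | 80.7% | −0.7 points |
| 0.02 | 2.872 | 81.4% | none |
| 0.05 | 2.917 | 82.6% | +1.2 points |
| 0.10 | 2.997 | 84.6% | +3.2 points |
| 0.20 | 3.179 | 88.5% | +7.1 points |

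**Step 4: break-even.** Adjustment pays when (1 − R2) × 155/152 is below 1, that is, when R2 exceeds 1 − 152/155 = 0.019. With age and sex only (two covariates, inflation 155/153 = 1.013, 154 df), break-even is 1 − 153/155 = 0.013, and power at R2 = 0 is 80.9%.

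**The case against.** The strongest reply is that the plan needs no repair. The randomised comparison is valid without covariates, its standard error already allows for chance imbalance, and the stated power is met without adjustment. The documents promise neither adjustment nor stratification, so the model breaks no commitment. All of this stands, and it limits the point to one of efficiency.

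The second reply is that nothing in the documents shows that age, sex or opioid intake predicts VAS on movement at 48 to 72 hours. This also stands. A reader might infer that precision is certainly being thrown away, or that adjustment is equivalent to 5% to 25% more patients at no cost, which is 1/(1 − R2) at R2 from 0.05 to 0.20. The documents do not support either inference: R2 is unknown, the range must include zero, and estimating the covariates costs about 2% of variance.

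The third reply concerns opioid dose. A reader might infer from the exclusion rule that every patient's daily dose is already on file. The rule needs only a yes/no check against 30 mg, and no section says that the dose is recorded. The same rule also truncates the range of doses, which may limit what the variable can explain. Only age and sex can be treated as available.

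What survives is the asymmetry: under one point of power is lost if the covariates predict nothing, against a gain of about one to seven points for R2 between 0.05 and 0.20.

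**Conclusion.** The point holds as a modest, optional improvement. The primary model omits age and sex although both are known for every patient, and the plan makes no other analytic use of them beyond summary and comparison between arms.

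It would be wrong to read this as a flaw in the validity of the primary analysis or in the sample size. The stated 80% reproduces at 80.9% to 81.4% for exactly the unadjusted comparison planned. It would also be too strong to say that adjustment removes chance imbalance, since it handles only the part captured by the modelled terms.

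The size is conditional: no gain at R2 of about 0.02, 82.6% power at 0.05, 84.6% at 0.10 and 88.5% at 0.20, with a floor of 80.7% if three covariates explain nothing. These figures rest on the assumed R2, a log-scale analysis, 40 evaluable patients per arm and a pooled four-arm error term.

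**What to change.** Before any outcome data are examined, amend section 7.0 so that the primary repeated-measures model includes age and sex as prespecified fixed effects alongside group, time and their interaction. State the form in which age enters, for example linear. Keep the unadjusted model as a named sensitivity analysis.

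Add preoperative daily opioid dose as a third covariate only if the dose itself is recorded for every patient before randomisation. That means one added data field, since the present eligibility rule needs only the threshold check. If the field is not added, stay with age and sex.

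The cost is a few lines of SAP text, two or three degrees of freedom (under one point of power if the covariates predict nothing) and possibly the one data field. Neither the sample size nor the randomisation changes.
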